3.8.3. Handling of Missing Data

For the primary and secondary efficacy endpoints, the primary analysis will be based on the mixed-effects model repeated measures (MMRM) method, which makes use of fully and partially observed data sequences from individual patients by estimating the covariance between data from different time points. The MMRM will be implemented using an unstructured approach to modeling both the treatment-by-time means and the (co)variances, leading to what is essentially a multivariate normal model wherein treatment arm means at the primary time point are adjusted to reflect both the actually observed data and the projected outcomes from the patients with missing data [11]. In this primary analysis, missing data will not be imputed and are assumed to be missing-at-random (MAR).

For the primary endpoint mNIS+7 and the first secondary endpoint Norfolk QOL, sensitivity analyses will be conducted to assess the impact of missing data as discussed in Section 4.3.

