4.3.1.1. Primary Analysis using MMRM Method for the mITT Population

The primary analysis will be performed using a restricted maximum likelihood (REML) based MMRM approach. The outcome variable is change from baseline in mNIS+7. The model includes baseline mNIS+7 score as a continuous covariate and fixed effect terms including treatment arm, visit (Month 9 or Month 18), treatment-by-visit interaction, genotype (V30M vs. non-V30M), age at hATTR Symptom onset (< 50 ; ≥ 50), region (North America, Western Europe, and Rest of World), and previous tetramer stabilizer use (yes vs. no). An unstructured covariance structure will be used to model the within-patient errors. The Satterthwaite approximation will be used to estimate the degrees of freedom. The primary comparison is the contrast (difference in least squares means [LS means]) between the patisiran and placebo groups at 18 months. Analysis will be implemented with SAS PROC MIXED.

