4.3.3. Exploratory Efficacy Evaluations

The continuous exploratory endpoints including grip strength, SGNFD, IENFD, dermal amyloid content, EQ-5D-5L index, EQ VAS, original NIS+7 and small/large fiber function (defined in Appendix 7.2.1) will be analyzed using an MMRM model similar to those employed for the primary analysis.

The categorical exploratory endpoints PND score and FAP stage will be descriptively summarized by presenting the number and percentage of patients in each category for each visit. The number of percentage of patients with improving, no change, and worsening in PND/FAP at each visit will also be summarized.

For EQ-5D-5L, a categorical summary of the numbers and percentages of patients reporting each ordinal response within each EQ-5D domain will be presented.

Cardiac structure and function will be assessed for all patients through echocardiograms. Cardiac stress and injury will be measured using serum levels of the cardiac biomarkers NT-proBNP and troponin I. Quantification of these biomarkers will be performed at a central laboratory. Descriptive statistics will be provided for actual values, changes, and percentage changes from baseline in echocardiogram parameters, serum levels of troponin I and NT-proBNP by treatment arm.

For cardiac subpopulation (defined in Section 4.2), the change from baseline to Month 18 in LV wall thickness, LV mass, LVEF, LV longitudinal strain, NT-proBNP and troponin I will be compared between the 2 treatment arms using MMRM. The model will include baseline value

as covariate and fixed effect terms including treatment arm, visit, and treatment-by-visit interaction.

All echocardiogram and cardiac function biomarkers data will be presented in data listings.

MR neurography data will be presented in a data listing.

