4.3.4. Subgroup Analyses

Subgroup analyses will be conducted to assess the consistency of treatment effect within various subgroups defined by the following baseline characteristics:

- Age [≥ 65 ; < 65 at randomization]
- Sex [Male; Female]
- Race [White; Non-White]
- Region [North America; Western Europe; Rest of World]
- NIS [< 50 ; ≥ 50]
- Genotype Class [Early-onset V30M; Other]
- Previous Tetramer Use [Yes; No]
- Genotype [V30M; non-V30M]
- FAP Stage [I; II & III]

Subgroup analyses will be performed for the primary endpoint mNIS+7 and Norfolk QOL-DN using MMRM models with baseline mNIS+7 score as a continuous covariate and genotype (V30M vs. non-V30M) as a factor. A forest plot will be generated to illustrate the estimated treatment effect along with 95% CI within each subgroup.

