5.4. Adjustment for Covariates in Statistical Models

The table below summarizes the history of changes in baseline covariates used in the statistical models.

Baseline Covariates	Protocol	SAP V1.0	SAP V2.0
	ANCOVA	ANCOVA	MMRM/ANCOVA
Baseline mNIS+7	X	X	X
Genotype (V30M vs. Non-V30M)	X		X
Genotype class (early onset V30M vs. Other)		X	
Age at hATTR symptom onset (< 50 vs. ≥ 50)			X
Previous tetramer stabilizer use (Yes vs. No)	X	X	X
Region (Western EU, North America, Rest of World)			X
Age at study entry as continuous variable	X		

Genotype class (early onset V30M vs. other) is one of the stratification factors at randomization. The early onset V30M subgroup includes patients who have the V30M genotype and were younger than 50 years old at hATTR amyloidosis symptom onset. At the time of this SAP amendment, the enrollment was complete and there were only 23 early onset V30M patients. Given the small sample size, the composite covariate “genotype class” is decomposed into 2 separate covariates “genotype” and “age at hATTR amyloidosis symptom onset.”

Region is added as a covariate because different rates of attrition and disease worsening were observed for different regions during blinded data monitoring. In addition, adding region may potentially address the influence of different non-V30M types observed across regions.

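### Region is added because attrition and worsening differ by region, but one region effect shared by Months 9 and 18 may not correct the Month 18 contrast; a region-by-visit term would

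*SAP*

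**What the plan says.** SAP 5.4 gives two reasons for adding region. One is regional differences in dropout and progression: "Region is added as a covariate because different rates of attrition and disease worsening were observed for different regions during blinded data monitoring". The other is mutation mix: "adding region may potentially address the influence of different non-V30M types observed across regions". It gives no figures by region or by arm.

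SAP 4.3.1.1 defines the primary model with "fixed effect terms including treatment arm, visit (Month 9 or Month 18), treatment-by-visit interaction, genotype (V30M vs. non-V30M"), followed by age at onset and then "region (North America, Western Europe, and Rest of World), and previous tetramer stabilizer use (yes vs. no"). Treatment-by-visit is the only interaction with visit. On covariance: "An unstructured covariance structure will be used to model the within-patient errors". SAP 3.8.3 adds: "In this primary analysis, missing data will not be imputed and are assumed to be missing-at-random (MAR").

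The secondary endpoints use a similar MMRM (SAP 4.3.2). Region is also in the imputation model and the Month 18 ANCOVA of two sensitivity analyses: MI/ANCOVA, imputed by arm, for mNIS+7 and Norfolk QOL-DN; and the pattern-mixture model for mNIS+7 (SAP 4.3.1.3 and 7.1). SAP Table 2 lists only the MMRM for NIS-W, R-ODS, walk speed, mBMI and COMPASS-31.

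**The concern.** In a progressive disease, a regional difference in rate of worsening most naturally means a gap in change from baseline that is larger at Month 18 than at Month 9. The model forces the two gaps to be equal. In a Month 18 ANCOVA, the method first planned, every covariate effect belongs to Month 18; after the change to MMRM it does not, although SAP 5.4 lists both models in one column.

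At stake is the Month 18 treatment difference under missing-at-random. If the faster-worsening regions lose a larger share of one arm, the observed Month 18 patients in the two arms differ in regional mix, and the model must correct for that with a term fitted mostly to Month 9.

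The documents make such a pattern plausible. Assessments after liver transplant, or after more than 14 days of tafamidis or diflunisal, are set to missing for mNIS+7, Norfolk QOL-DN and NIS-W (SAP 3.7). Tafamidis is described as approved in the EU but not the US (SAP 1.1.1), and rapid progression opens the option of other treatment (SAP 1.2.3).

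**Working it through.** **Inputs.** From the documents: effect 8.95, Month 18 SD 16, 154 evaluable patients, 25% discontinuation (SAP 3.1); 2:1 allocation (SAP 1.2.2). Assumed: Month 9 SD 10, correlation 0.69 or 0.7, and all regional shares, gaps and missingness rates.

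**1. The plan's own figure.** Placebo n = (1.960 + 1.282)² × 16² × (1 + 1/2) / 8.95² = 10.51 × 384 / 80.10 = 50.4, so 51 placebo and 153 in total, against 154 stated. With 51 and 103 patients, a noncentral t gives 90.1% power. 154 / 0.75 = 205.3, against approximately 200. The figures reproduce.

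**2. What a shared effect can correct.** For a patient seen at Month 9 but not at Month 18, the model projects with slope b = ρ × SD18 / SD9 = 0.69 × 16 / 10 = 1.104. Let G9 and G18 be the regional gaps and r the shared region effect. The gap left uncorrected at Month 18 is (G18 − r) − b(G9 − r) = (G18 − b·G9) − (1 − b)·r. With b near 1, r hardly matters.

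The generalised least squares weight of Month 9 in r is (256 − 110.4) / (356 − 220.8) = 1.08, leaving −0.08 for Month 18 (0.90 and 0.10 at correlation 0.5). With G18 = 2·G9, r ≈ 1.08·G9 − 0.16·G9 = 0.92·G9. The uncorrected gap is then 0.896·G9 without region and 0.896·G9 + 0.104 × 0.92·G9 = 0.99·G9 with the main effect.

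**3. Strong scenario.** A fast region holds 35% of patients. Month 18 missingness there and elsewhere is 20% and 15% on patisiran, 55% and 30% on placebo (24% overall). The fast region's share of observed patients is:
- patisiran: 0.35 × 0.80 / (0.35 × 0.80 + 0.65 × 0.85) = 0.2800 / 0.8325 = 0.336
- placebo: 0.35 × 0.45 / (0.35 × 0.45 + 0.65 × 0.70) = 0.1575 / 0.6125 = 0.257

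Bias ≈ uncorrected gap × (0.336 − 0.257) = uncorrected gap × 0.079.

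| Gap at Month 9 | Formula, no region | Formula, main effect | Simulated excess over region-by-visit, no region | Simulated excess, main effect |
|---|---|---|---|---|
| 3 | 0.21 | 0.24 | 0.23 | 0.24 |
| 5 | 0.35 | 0.39 | 0.35 | 0.40 |
| 8 | 0.57 | 0.63 | 0.54 | 0.65 |

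The simulation used 1,500 trials of 200 patients. Separate reruns gave main-effect bias of 0.24 to 0.27, 0.36, and 0.58 to 0.71, with region-by-visit near 0. With milder missingness (patisiran 25% and 15%, placebo 35% and 20%), the simulated excess was about 0.1.

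**4. Wider scenarios.** Three regions (40/30/30%), placebo progression 15/24/36 points, half of it by Month 9, 40% of dropouts before Month 9, very large samples. Entries are bias against −8.95; positive means benefit understated. The last column is a regression-imputation stand-in for MI/ANCOVA.

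| Dropout by region | No region | Main effect (SAP) | Region-by-visit | By-arm imputation |
|---|---|---|---|---|
| (a) Both arms 10/25/45% | +0.03 | +0.05 | +0.05 | +0.05 |
| (b) Placebo 15/35/60%, patisiran 5/8/12% | +1.19 | +1.09 | −0.02 | −0.02 |
| (c) Placebo 15/35/60%, patisiran 10/20/30% | +0.83 | +0.77 | −0.02 | −0.02 |
| (d) As (b), arms swapped | −1.25 | −1.14 | −0.04 | −0.04 |
| (e) As (b), gap equal at both visits | +0.51 | −0.02 | −0.02 | −0.03 |
| (f) Progression 20/24/29; placebo 15/25/35%, patisiran 5/8/10% | +0.15 | +0.12 | −0.04 | −0.04 |
| (g) As (b), wider regional spread | +1.60 | +1.51 | +0.01 | not run |
| (h) As (b), all loss before Month 9 | +2.22 | +1.21 | +0.01 | not run |
| (i) As (b), effect proportional to regional progression | +1.32 | +1.24 | +0.45 | +0.01 |

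At N = 200 under (b), power was 79% with the main effect and 90% with region-by-visit. With no true effect, rejection was 7.3% and 5.7% (Monte Carlo SE about 0.6 percentage points).

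**5. Precision.** At N = 200 the SE went from 2.61 to 2.58 with a 5-point gap and from 2.74 to 2.64 under (a). With no gap there was no loss.

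The simulations left out the other covariates and used maximum likelihood, not REML with Satterthwaite degrees of freedom.

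**The case against.** The strongest reply is that nothing in the documents shows the bias exists. It needs both a widening gap and regional attrition that differs by arm. Blinded monitoring cannot show the second, and the first is read into the word rates. SAP 5.4 does not say that region was added to support missing-at-random, and it gives a second reason. The larger biases need strong assumptions, such as 55% loss on placebo in one region. When dropout followed Month 9 change by the same rule in both arms, the excess over region-by-visit was only about 0.05 to 0.23 points. If placebo loses more, the error runs against patisiran. All of this stands.

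The reply also points to MI/ANCOVA, which gives region its own Month 18 coefficient in each arm and was unbiased within 0.05 points wherever its stand-in was run. That stands for mNIS+7 and Norfolk QOL-DN, with two limits. NIS-W, which shares the censoring rule, and the later secondary endpoints have no such analysis. And MI/ANCOVA differs from the MMRM in other covariates too, while the pattern-mixture model imputes off-treatment patisiran values from placebo, so a discrepancy would not point to region alone.

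A reader might also infer that the subgroup and cardiac models need region, since SAP 4.3.4 specifies "using MMRM models with baseline mNIS+7 score as a continuous covariate and genotype (V30M vs. non-V30M) as a factor" and SAP 4.3.3 only the baseline value "as covariate and fixed effect terms including treatment arm, visit, and treatment-by-visit interaction". The documents do not support making that part of this point. Those analyses assess consistency or are exploratory, do not touch the primary test, and no bias was quantified for them. Region is constant within the region subgroups, and only 23 patients are early-onset V30M.

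**Conclusion.** The point holds as a conditional weakness. A reader might infer that the primary analysis is biased by regional attrition; the documents do not show that. They show a covariate added for a reason its form may not serve.

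Relative to 8.95 points, the strong scenario (0.24 to 0.65) is 3 to 7%, and the widest case (1.51) is 17%. The main effect is adequate if the gap is constant over visits, and the contrast is unbiased if attrition matches across arms. The main effect does remove close to half of the bias when all loss precedes Month 9 (2.22 to 1.21); in the other widening-gap cases with unequal attrition it removes little or none. Region-by-visit removed the bias in every case except where the treatment effect itself varied by region (+0.45 left). All sizes rest on assumed regional inputs. The change is worth making because the region-by-visit model contains the SAP model as a special case.

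**What to change.** Before unblinding, add a region-by-visit interaction to the MMRM in SAP 4.3.1.1 and to the secondary MMRMs built on it in SAP 4.3.2. Leave the subgroup and cardiac models as they are.

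The cost is SAP wording and no new data. With three regions, the extra parameters are (3 − 1) × (2 − 1) = 2 for two-visit endpoints and (3 − 1) × (5 − 1) = 8 for mBMI, which has five post-baseline visits. No loss of precision is expected, and a slight gain if the regional gap widens.

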5.5. Binary Analysis of mNIS+7

In SAP V1.0, binary analysis of mNIS+7 included an analysis of patients with < 2-point increase in mNIS+7 change from baseline at Month 18. The 2-point threshold was originally used in the tafamidis Phase 3 trial in hATTR amyloidosis patients with polyneuropathy to define responders for the NIS-LL co-primary endpoint. That trial enrolled patients with very early stage neuropathy and mean baseline NIS-LL of approximately 8-11 points, in whom a 2-point worsening of NIS-LL was considered to be clinically meaningful. However, the patients enrolled onto this study have more advanced disease, with a mean baseline NIS of approximately 60 points, and the mNIS+7 primary endpoint is very different from NIS-LL, with a maximum score of 304 points compared to 88 points for NIS-LL. Therefore, a 2-point threshold was not deemed relevant for mNIS+7 change in this patient population.

In this SAP V2.0, 2 thresholds, < 10-point increase and any decrease (< 0-point change from baseline) will be employed to conduct the binary analysis of mNIS+7. These thresholds of < 10-point and < 0-point were chosen based on the 18-month estimated mNIS+7 progression rate observed in a natural history study of hATTR amyloidosis patients and the observed effect of patisiran on mNIS+7 at 18 months in the Phase 2 OLE study, respectively.

5.6. Censoring Data Post Alternative FAP Treatment

In this SAP V2.0, for the primary analysis of mNIS+7 and Norfolk QoL, the data post alternative FAP treatment will be censored. This censoring rule was not previously specified in the protocol or SAP V1.0. The rationale of adding this censoring rule is to eliminate the potential confounding effect caused by alternative FAP treatment. Sensitivity analyses for mNIS+7 and Norfolk QoL will be conducted including data post alternative FAP treatment.

In SAP V2.1, an update was made to apply the censoring rule to NIS-W as well so that the results will be consistent with the component analysis of mNIS+7.

For all other efficacy endpoints, the data will not be censored since no sensitivity analyses are planned.

5.7. Other Changes

Additional changes are listed in the table below.

Change from Protocol and/or SAP V1.0	Detailed Description/Rationale
In the protocol and original SAP V1.0, the first day of drug administration was designated as Day 0. In this SAP amendment and the TLF outputs, the first dose day will be defined as Day 1.	The change is made to follow CDISC convention. Each calculated study day after dosing is 1 day plus the reported study day following the protocol defined Schedule of Assessments.
In the protocol and original SAP V1.0, it was intended that an interim analysis for sample size re-estimation would be conducted; however, no interim analysis was conducted during the study.	In 2013, Berk et al. published results of a randomized placebo-controlled trial of diflunisal in FAP. This trial demonstrated that efficacy using a composite neurologic impairment score primary endpoint (NIS+7) could be established in a similar population with a similar study design and smaller study size (N=130). The sponsor believed that an interim analysis for sample size reassessment was therefore no longer necessary.
In SAP V2.0, dermal amyloid content is added as an exploratory endpoint.	In addition to IENFD and SGNFD, skin punch biopsies will also be assessed for dermal amyloid content, which has been added as an efficacy parameter in this SAP V2.0.
In SAP V2.0, the walk speed for patients unable to perform the walk will be imputed as 0.	The imputation algorithm is added to address the informative missing data for patients unable to perform the walk due to worsening of disease.
Renal clearance for siRNA and 4-dimethylaminobutyric acid (DMBA) will not be analyzed.	As per protocol, renal clearance for siRNA and 4-dimethylaminobutyric acid (DMBA) were to be determined whenever possible. Only sparse pre-dose urine collections (and volumes) were obtained in patients enrolled in this study on select days that patients returned to the clinic for dosing (Days 0, 21, 126, 252, 399, 546 and at time of early withdrawal). In order to estimate renal clearance, detailed serial urine and corresponding plasma collections that describe a time course of exposures in both matrices over a dosing interval within individual subjects are required. As it is not possible to reliably estimate the renal clearance for either siRNA or DMBA in individual patients using standard pharmacokinetic methods based on the limited urine and plasma sampling implemented in this outpatient study, renal clearance estimation for either analyte were not performed and cannot be reported for this study.

Change from Protocol and/or SAP V1.0	Detailed Description/Rationale
In SAP V2.0, the definition for cardiac subpopulation was added. This subpopulation was not previously defined in the protocol or in SAP V1.0.	In SAP V2.0, the cardiac subpopulation was defined in Section 4.2 as the following: the cardiac subpopulation will be comprised of patients with pre-existing cardiac amyloid involvement, defined as patients with baseline left ventricular (LV) wall thickness ≥ 1.3 cm and no aortic valve disease or hypertension in medical history.
